8.2 ADVERSE EVENTS AND SERIOUS ADVERSE EVENTS

8.2.1 DEFINITION OF ADVERSE EVENTS (AE)

An Adverse Event (AE) is any untoward medical occurrence associated with the use of an intervention in a study participant, which does not necessarily have a causal relationship with the intervention. An AE can therefore be any unfavourable and unintended sign, symptom or disease temporally associated with the use of the DB, whether or not considered related to the investigational intervention.

Stable chronic conditions which are present prior to entry in the study and do not worsen are not considered AE. These pre-existing conditions will be documented in the participant's medical history.

8.2.2 DEFINITION OF SERIOUS ADVERSE EVENTS (SAE)

AE are classified as serious or non-serious. A Serious Adverse Event is any AE that is:

- 1. fatal
- 2. life-threatening
- 3. requires or prolongs inpatient hospital stay
- 4. results in persistent or significant disability or incapacity
- 5. a congenital anomaly or birth defect
- 6. an important medical event

The term "life-threatening" in the definition of "serious" refers to an AE in which the participant was at risk of death at the time of the event. It does not refer to an AE that hypothetically might have caused death if it were more severe.

Important medical events are those that may not be immediately life threatening but are clearly of major clinical significance. They may jeopardize the participant and may require intervention to prevent one of the other serious outcomes noted above.

We do not foresee any SAEs occurring that are related to the use of the DB. That being said, all SEAs will be documented and reported for any incident that:

- (a) is related to a failure of the dynamic bar or a deterioration in its effectiveness, or any inadequacy in its directions for use; and
- (b) has led to the death or a serious deterioration in the state of health of a patient, user or other person, or could do so were it to recur. "Serious deterioration in the state of health" means: a life-threatening disease, disorder or abnormal physical state; the permanent impairment of a body function or permanent damage to a body structure; or a condition that necessitates an unexpected medical or surgical intervention to prevent such a disease, disorder or abnormal physical state or permanent impairment or damage.

8.2.3 ADVERSE EVENT REPORTING

Known risks associated with all standard bars include pressure sores, skin rashes, unintentional selfinjuries, and clubfoot recurrence for suboptimal brace wear or application.

We anticipate that the same risks are associated with the dynamic bar prototype, in addition to the risk of bar malfunction or breakage due to lack of extensive material evaluations, and an increased risk of clubfoot recurrence due to the unprecedented mobility provided to patients.

If any of these events occur during the study, they will be documented in the patient's chart, and on REDCap as specified by the Clubfoot Research Registry protocol. These events might also result in the participant being withdrawn from the study or temporarily discontinued from the study intervention.

It should be noted that pressure sores may break skin. While patients are encouraged to wear socks with their boots, if they choose to not wear socks, this may result in the ShearBan adhesive, which will be placed on top of the temperature sensor inside the boot, coming into contact with intact or non-intact skin.

8.2.4 CLASSIFICATION OF AN ADVERSE EVENT

8.2.4.1 SEVERITY OF EVENT

The severity of an AE will be assessed by a blinded outcomes assessor, physiotherapist [name], and/or the PI. They will use the following definitions when assessing the intensity of an AE:

- Mild Events require minimal or no treatment and do not interfere with the participant's daily activities.
- **Moderate** Events result in a low level of inconvenience or concern with the therapeutic measures. Moderate events may cause some interference with functioning.

• Severe – Events interrupt a participant's usual daily activity and may require systemic drug therapy or other treatment. Severe events are usually potentially life-threatening or incapacitating. Of note, the term "severe" does not necessarily equate to "serious".

The only "severe" AE that is foreseen to potentially occur during the study is clubfoot recurrence. Clubfoot recurrence would likely be treated by serial casting, as is standard care for clubfoot treatment. Mild to moderate AEs may potentially include pressure sores, skin rashes, and unintentional selfinjuries. All of these AEs are known risks associated with FABs.

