8.2.4.2 RELATIONSHIP TO DYNAMIC BAR OR STANDARD BAR

All Adverse Events (AEs) will have their relationship to the DB or SB assessed by the blinded outcomes assessor, physiotherapist [name], and/or the PI, based on temporal relationship and their clinical judgment. The degree of certainty about causality will be graded using the categories below.

- **Definitely Related** There is clear evidence to suggest a causal relationship, and other possible contributing factors can be ruled out. The clinical event occurs in a plausible time relationship to study intervention administration and cannot be explained by concurrent disease or other drugs or chemicals. The response to withdrawal of the study intervention should be clinically plausible.
- **Probably Related** There is evidence to suggest a causal relationship, and the influence of other factors is unlikely. The clinical event occurs within a reasonable time after administration of the study intervention, is unlikely to be attributed to concurrent disease or other drugs or chemicals, and follows a clinically reasonable response on withdrawal.
- **Possibly Related** There is some evidence to suggest a causal relationship (e.g., the event occurred within a reasonable time after administration of the study intervention). However, other factors may have contributed to the event (e.g., the participant's clinical condition, other concomitant events).
- Unlikely to be related A clinical event whose temporal relationship to study intervention administration makes a causal relationship improbable (e.g., the event did not occur within a reasonable time after administration of the study intervention) and in which other drugs or chemicals or underlying disease provides plausible explanations (e.g., the participant's clinical condition, other concomitant treatments).
- **Unrelated** The AE is completely independent of study intervention administration, and/or evidence exists that the event is definitely related to another etiology.

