8.2.4.3 EXPECTEDNESS

The blinded outcomes assessor, physiotherapist [name], and/or the PI, will be responsible for determining whether an Adverse Event (AE) is expected or unexpected. An AE will be considered unexpected if the nature, severity, or frequency of the event is not consistent with the risk information previously described for the study intervention.

All unexpected AEs will be reported to The Hospital for Sick Children Research Ethics Board according to The Hospital for Sick Children's Adverse Event Reporting Requirements.

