10.1.6 CONFLICT OF INTEREST POLICY

There is a conflict of interest wherein the PI and co-investigators of this study are the inventors of the dynamic bar, and so they might wish to sell the bar in the future for profit. This conflict of interest will be mitigated by relying on unbiased quantitative evaluations done by blinded outcomes assessors in order to assess the study's endpoints.

There is also a potential pre-existing health care provider-patient relationship between members of the care team and the participant. However, this potential conflict of interest will be mitigated through exclusion of the circle of care team from the informed consent process. The research assistant and/or research coordinator will be responsible for obtaining informed consent.

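### The PI, an inventor of the bar who is not described as blinded, may alone grade severity, relatedness and expectedness of adverse events, and the conflict-of-interest mitigation does not cover this

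*Combined protocol and SAP*

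**What the plan says.** Three subsections say who judges an adverse event (AE), each with the same list of people.

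- Severity (8.2.4.1) opens with "The severity of an AE will be assessed by a blinded outcomes assessor"; with its full list of graders the sentence reads "The severity of an AE will be assessed by a blinded outcomes assessor, physiotherapist [name], and/or the PI".
- Relatedness (8.2.4.2): "All Adverse Events (AEs) will have their relationship to the DB or SB assessed by the blinded outcomes assessor, physiotherapist [name], and/or the PI".
- Expectedness (8.2.4.3): "The blinded outcomes assessor, physiotherapist [name], and/or the PI, will be responsible for determining whether an Adverse Event (AE) is expected or unexpected".

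Section 10.1.6 declares that "the PI and co-investigators of this study are the inventors of the dynamic bar" and that they might later sell it for profit. The remedy it offers is this: "This conflict of interest will be mitigated by relying on unbiased quantitative evaluations done by blinded outcomes assessors".

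Section 6.3 blinds the outcomes assessor and nobody else. Under 4.1 the PI and/or a physiotherapist monitors brace fit, so the PI can see which bar a child wears.

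**The concern.** The list is joined by 'and/or', so a grade by any one person on it satisfies the text. Nothing requires the blinded assessor to take part, gives one grader precedence, or says how a disagreement is settled. The safety grades for a new device may therefore rest only on someone who knows the allocation and has a declared interest in the result.

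The relatedness task raises a second difficulty. The blinded assessor is asked to relate events to the DB or to the standard bar (SB). For some events that cannot be done without learning the allocation, and the same assessor's blind protects the recurrence endpoint. The plan does not say which events the assessor should leave to someone else, or to whom they should go.

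**Working it through.** No arithmetic applies: the plan gives no figure on this point. The check sets the sections side by side.

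**1. Can the PI grade alone?** Yes, for all three judgements. The list could be read with the physiotherapist as the blinded assessor (6.3 says the assessor is a physiotherapist) or as a separate person. The PI is permitted under either reading.

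**2. Is the PI free of the conflict, or blinded?** Neither is stated. 10.1.6 declares the conflict, 6.3 blinds only the assessor, and 4.1 allows the PI to monitor fit.

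**3. Does the mitigation reach these grades?** 10.1.6 relies on evaluations "done by blinded outcomes assessors in order to assess the study's endpoints". The endpoints in Section 3 are recruitment, dropout and related survey responses, comfort, wear hours and recurrence. AE severity, relatedness and expectedness are not among them. Sections 2.3 and 4.1 have the blinded assessor examine children for recurrence and complications, but finding a complication and grading it are separate acts, and 8.2.4 does not tie the second to the first.

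**4. What depends on the grades?**

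- *Severity and relatedness together.* Under 6.3, any severe AE related to the DB leads to unblinding for all participants. The only severe AE foreseen in 8.2.4.1 is recurrence, which is also the third secondary endpoint. For a recurrence in a DB child, relatedness is then the open half of the trigger. The DB arm has 10 planned children, and one such grade affects the blind for all 20. Later examinations feed the recurrence comparison in 9.3.3 (more than 2 further instances in the DB arm).
- *Expectedness.* 8.2.4.3 has unexpected AEs reported to the Research Ethics Board (REB). 8.2.3 already anticipates breakage and a raised recurrence risk with the DB, without frequencies, so the judgement leaves room for discretion.

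**5. Which relatedness judgements can be made blind?**

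| Event | Risk of | Blind judgement possible? |
|---|---|---|
| Pressure sores, rashes, self-injury, recurrence (8.2.3) | Both bars | Yes, as relation to the assigned bar |
| Malfunction or breakage of the DB (8.2.3) | Listed as an additional DB risk | No, the event itself identifies the bar |
| Event after Day 30, to be attributed to one bar and not the other | Depends on arm, since DB children return to the SB (4.1) | No |

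**6. What safeguards exist?** All AEs and serious AEs are documented regardless of relationship (8.2.5). The Data Safety Monitoring Board (DSMB) and REB are told of any AE or unblinding (6.3). The DSMB is independent of study conduct and meets once in the 90-day period (10.1.4). These keep the event on record and visible. None of them supplies an unconflicted grade.

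**The case against.** The strongest reply is that little harm can follow. Events are recorded whatever the grade, and 6.3 has the DSMB and REB notified of any AE, so a favourable grade does not hide an event. Unblinding also requires the blinded assessor to notify the study team. Recurrence is defined by examination criteria that the blinded assessor applies, so a PI grade would not change the recurrence count. The primary endpoint is feasibility.

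All of that stands, and it limits the point. It does not answer it: the relatedness half of the unblinding trigger can still rest on the PI alone, and no safeguard requires an independent grade.

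Some stronger readings are tempting, but the documents do not support them:

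- *That the PI's role contradicts 10.1.6, or that the plan claims to have removed the conflict.* The plan says mitigated, and only for endpoints. This is a gap in coverage.
- *That expectedness alone decides what reaches the REB.* 8.2.4.3 read alone suggests so, but 6.3 has the REB notified of any AE. The two sections need reconciling.
- *That regrading one event among 10 DB children shifts the DB event rate by 10 points.* Regrading leaves the overall AE rate unchanged. It moves only a count within a grade, and Section 9.3 plans no analysis by grade.
- *That a blinded assessor can never judge relatedness.* For risks common to both bars this is possible from timing and clinical judgement, as 8.2.4.2 provides.

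It is also fair to object to making a DSMB member the routine grader. That would draw the member into study conduct, against 10.1.4, and have the board review its own grades.

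**Conclusion.** The point holds as a gap in three subsections. A conflicted person who is not described as blinded may alone decide severity, relatedness and expectedness, and the stated mitigation does not extend to those decisions. The practical weight lies in the rule in 6.3, where one severe event judged related to the DB is enough to end the blind for every participant.

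The size of any bias cannot be estimated from the documents. The primary endpoint is unaffected and the recurrence count is not directly altered, so this is an inexpensive improvement to make before enrolment.

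The conclusion assumes that 'and/or' has its ordinary meaning, that the PI is in practice unblinded (the protocol never says otherwise), and that a clinician who is not an inventor is available. The protocol does not say whether the named physiotherapist is a co-inventor, so the sponsor must confirm this before relying on that person.

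**What to change.** 1. **8.2.4.1.** Make the blinded outcomes assessor, working without bar information, the required primary grader of severity. The assessor already examines every child at each visit. Keep any PI grade as a separate record that does not override the assessor's.
2. **8.2.4.2 and 8.2.4.3.** Do not allow the PI or a co-inventor to be the sole grader. The blinded assessor judges relation to the assigned bar, without being told which bar it is. Judgements that need the bar's identity, such as those on DB breakage, go to a clinician already involved in the trial who is not an inventor. The DSMB sees the grades at its planned review and does not act as routine grader.
3. **6.3 and 8.2.4.3.** Reconcile notification of the REB and DSMB for any AE with REB reporting specified for unexpected AEs.

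The cost is revised wording in these sections and slightly more work for the assessor. No visit, examination or sample size changes.

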8.2.4.2 RELATIONSHIP TO DYNAMIC BAR OR STANDARD BAR

All Adverse Events (AEs) will have their relationship to the DB or SB assessed by the blinded outcomes assessor, physiotherapist [name], and/or the PI, based on temporal relationship and their clinical judgment. The degree of certainty about causality will be graded using the categories below.

- **Definitely Related** There is clear evidence to suggest a causal relationship, and other possible contributing factors can be ruled out. The clinical event occurs in a plausible time relationship to study intervention administration and cannot be explained by concurrent disease or other drugs or chemicals. The response to withdrawal of the study intervention should be clinically plausible.
- **Probably Related** There is evidence to suggest a causal relationship, and the influence of other factors is unlikely. The clinical event occurs within a reasonable time after administration of the study intervention, is unlikely to be attributed to concurrent disease or other drugs or chemicals, and follows a clinically reasonable response on withdrawal.
- **Possibly Related** There is some evidence to suggest a causal relationship (e.g., the event occurred within a reasonable time after administration of the study intervention). However, other factors may have contributed to the event (e.g., the participant's clinical condition, other concomitant events).
- Unlikely to be related A clinical event whose temporal relationship to study intervention administration makes a causal relationship improbable (e.g., the event did not occur within a reasonable time after administration of the study intervention) and in which other drugs or chemicals or underlying disease provides plausible explanations (e.g., the participant's clinical condition, other concomitant treatments).
- **Unrelated** The AE is completely independent of study intervention administration, and/or evidence exists that the event is definitely related to another etiology.

8.2.4.3 EXPECTEDNESS

The blinded outcomes assessor, physiotherapist [name], and/or the PI, will be responsible for determining whether an Adverse Event (AE) is expected or unexpected. An AE will be considered unexpected if the nature, severity, or frequency of the event is not consistent with the risk information previously described for the study intervention.

All unexpected AEs will be reported to The Hospital for Sick Children Research Ethics Board according to The Hospital for Sick Children's Adverse Event Reporting Requirements.

8.2.5 TIME PERIOD AND FREQUENCY FOR EVENT ASSESSMENT AND FOLLOW-UP

All AEs and SAEs occurring while on study will be documented regardless of relationship. Information to be collected will include event description, date of onset, date of resolution, outcome, and the assessment of seriousness, expectedness, relationship to study intervention, and severity.

Any baseline condition recorded in the medical history that deteriorates at any time during the study, will be recorded as an AE or SAE.

Changes in the severity of an AE will be documented to allow an assessment of the duration of the event at each level of severity to be performed.

Events will be followed for outcome information until resolution or in the opinion of the blinded outcomes assessor, physiotherapist [name], and/or the PI, the participant is stable and does not require further follow-up, or the participant is deemed lost to follow-up.

8.2.6 REPORTING EVENTS TO PARTICIPANTS

Participants and/or their parent/legal guardian will be informed in a timely manner of any new information, including safety information, that is relevant to that participant's willingness to continue participation. The communication of this information will be documented through a revised REB approved Informed Consent Form, where possible, based on the timeliness of the information.

9 STATISTICAL CONSIDERATIONS

9.1 SAMPLE SIZE DETERMINATION

The intent of this study is to obtain preliminary data on the current prototype and evaluate the feasibility of conducting a larger-scale clinical trial. Therefore, only a minimum of 10 patients will be enrolled in each arm.

In a future effectiveness randomized controlled trial, we plan to use a sample size of 124, with 62 patients per arm. This sample size will ensure that the study has sufficient statistical power to detect a minimal clinically detectable difference in recurrence rates of at least 20% between the SB and DB group. Note this is assuming that the recurrence rates in the control arm will be 30%, as reported recurrence rates after correction range from 20-41% (6). This power analysis was conducted based on 80% power and 5% type 1 error.

The Clubfoot Clinic at SickKids sees approximately 35 patients per week. Based on the frequency of clinical visits required for patients at different stages in the Ponseti treatment, it is expected that approximately 15% of these patients will be between the ages of 1 and 3 and in the minimum 12-hour per day bracing stage of the Ponseti treatment. Furthermore, approximately 80% of all clubfoot patients are idiopathic, and it is expected that 75% of eligible patients will be willing to participate in the trial (22). Therefore, it is foreseen that it will take approximately 2 months to register all 20 participants.

9.2 POPULATIONS FOR ANALYSES

The following study populations are defined and will be analyzed as specified below:

- Intent to treat population: the total population of patients registered in the study.
- Experimental arm population: all registered participants in the experimental arm with DB.
- Control arm population: all registered participants in the control arm with SB.

- Safety population: all registered participants who wore their FAB as prescribed for the full 90-day study period.
- Brace discomfort population: all registered participants who have any history of brace intolerance or indicated in the parent-reported survey that they are not comfortable/have concerns with their original FAB.
- Brace comfort population: all registered participants who have no history of brace intolerance and indicated in the parent-reported survey that they are comfortable/have no concerns with their original FAB.

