2.3 RISK/BENEFIT ASSESSMENT

This DB has the potential to greatly improve patient and parent experience with clubfoot bracing during the night-time phase of treatment. By increasing the patient's independent leg motion and comfort, brace tolerance should improve, and in turn, reduce the risk of relapse. By increasing brace wear, brace comfort and minimizing recurrence, this new bar design should lead to improved clinical outcomes, as well as patient and parent-reported outcomes.

The risks associated with the use of the DB prototypes includes all the risks associated with SBs, such as pressure sores and skin rashes. Additional risks associated with the DB might include bar malfunction or breakage, due to lack of extensive material evaluations. Clubfoot recurrence still occurs with the SB, but the risk may be increased with the DB as it will give patients unprecedented mobility. Walking in any foot abduction brace is not recommended, however the added mobility provided by the DB might enable safer mobility for the child possibly preventing injury and falls. To mitigate risks and complications, a blinded outcomes assessor will regularly evaluate the patients, and if any sign of clubfoot recurrence is observed, the child will immediately return to their original FAB with serial casting

as needed. The intervention period in this feasibility study is purposely short to avoid placing a child in a potentially ineffective brace for a prolonged period of time.

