6.3 MEASURES TO MINIMIZE BIAS: RANDOMIZATION AND BLINDING

Each patient will be assigned a unique study ID. Patients will be assigned to an arm by drawing lots. This will be done by preparing 20 opaque, sealed envelopes. 10 of these envelopes will contain the word "Experimental," and the remaining 10 will contain the word "Control." On Day 0 of the study period, each participant will choose an envelope at random, and be assigned to that arm. This technique will ensure that the ratio between patients in each arm is 1:1.

To minimize bias, the outcomes assessor, who is an advanced practice physiotherapist clubfoot provider, will be independent of the study and design teams and blinded, so they will not know which bar has been assigned to which patient.

To ensure that the outcomes assessor remains blinded, a member of the study team will check in the patient at the beginning of each visit, remind the patient and parent about the blinding, and ensure that the bar is removed and hidden from view before the outcome assessor enters the evaluation room.

Unblinding may occur for any participant who has experienced an adverse event, such as clubfoot recurrence, and must return to their original SB, if not already using it. Unblinding will occur for all participants if any severe adverse event occurs that is related to the use of the DB. For unblinding to occur, the outcomes assessor must notify a member of the study team, and any member of the study team may unblind the outcomes assessor.

All intentional and unintentional breaking of the blind will be documented in the study's enrollment log, along with the reason(s) for unblinding. Per protocol, the Data Safety Monitoring Board and Research Ethics Board will also be notified of any adverse events or unblinding.

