7.2 PARTICIPANT DISCONTINUATION/ WITHDRAWAL FROM THE STUDY

Participants are free to withdraw from participation in the study at any time upon request. An Investigator may discontinue or withdraw a participant from the study for the following reasons:

- Withdrawal of informed consent (participant or parent/guardian withdraw for any reason)
- If any clinical Adverse Event (AE), laboratory abnormality, or other medical condition or situation occurs such that continued participation in the study would not be in the best interest of the participant.
- If the participant meets an exclusion criterion (either newly developed or not previously recognized) that precludes further study participation.

The reason for participant discontinuation or withdrawal from the study will be recorded in the study enrollment log. Patients who do not follow the prescribed bracing schedule will still be included in the study and recorded with the intention to treat principle. Similarly, if the DB prototype breaks or malfunctions and cannot be quickly repaired, the patient will return to their original SB but will not be withdrawn from the study.

Participants who sign the informed consent form, but do not return for study visits 1, 2 and/or 3 will be replaced. Participants who sign the informed consent form, and return for study visits 1, 2 and 3 but subsequently withdraw, or are withdrawn or discontinued from the study will not be replaced. The data from participants who are withdrawn or discontinued from the study will be used in the analysis unless the participant requests otherwise.

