9.3.3 ANALYSIS OF THE SECONDARY ENDPOINTS

Parent-reported comfort levels will be determined by parent-reported surveys with 5-point Likert scale responses. Results from these surveys will be analyzed with descriptive statistics for the intent to treat population, the brace discomfort population, and the brace comfort population.

Daily bracing times will be measured by a temperature sensor added in each patient's boots for the entire 90-day study period. The number of hours the brace is worn per day will be divided by the standard number of desirable hours in brace (12 hours) in order to obtain a fraction that quantifies the patient's adherence to the FAB. Mean 'adherence fractions' will be calculated for patients in each arm, and then compared using descriptive statistics. This analysis will be performed for the intent to treat population, the brace discomfort population, and the brace comfort population. This data will be compared to the self-reported brace wear hours by parents in their daily logs.

To ensure minimal efficacy of the DB prototype, all signs of clubfoot recurrence will be carefully examined at each study visit. The null hypothesis is that 'the dynamic bar does not lead to higher rates

of clubfoot recurrence,' and it will be rejected if the number of patients in the safety population that develop clubfoot recurrence during the 90-day study period, is substantially greater in the experimental arm than it is in the control arm (i.e. more than 2 instances of clubfoot recurrence in the experimental arm than in the control arm). Note that this endpoint is not intended to prove safety or efficacy, but rather to ensure that the design may prevent early recurrence before a larger-scale trial is conducted. Clubfoot recurrence is defined as a Pirani score > 0.5, a new occurrence of cavus, adduction and/or hindfoot varus, or a loss of passive ankle dorsiflexion (equinus) of < 10 degrees above neutral or a reduction of 5 or more degrees from the previous visit. Note that all clinical tests required to diagnose recurrence are routinely performed as standard clubfoot care.

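### The numeric recurrence rule counts only children who wore the brace as prescribed for all 90 days, so early recurrences that are cast or withdrawn can leave the count

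*Combined protocol and SAP*

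**What the plan says.** Section 9.2 defines the set: "Safety population: all registered participants who wore their FAB as prescribed for the full 90-day study period". What counts as wearing the brace as prescribed is not defined.

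Section 9.3.3 states the null hypothesis that the dynamic bar (DB) does not raise recurrence. Its condition for rejection begins: "it will be rejected if the number of patients in the safety population that develop clubfoot recurrence during the 90-day study period". The DB count must then clearly exceed the control count, and a parenthesis makes this an excess of more than 2, that is, 3 or more. Recurrence is looked for at every visit.

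The same section treats wear time differently: "This analysis will be performed for the intent to treat population, the brace discomfort population, and the brace comfort population". Comfort is also analysed by intent to treat. No section gives a recurrence comparison for all randomised children.

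Three places say what follows a recurrence:

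- Section 2.3: "if any sign of clubfoot recurrence is observed, the child will immediately return to their original FAB with serial casting", the casting being qualified as needed.
- Section 8.2.4.1: "Clubfoot recurrence would likely be treated by serial casting, as is standard care for clubfoot treatment".
- Section 8.2.3, on a list of events that includes recurrence: "These events might also result in the participant being withdrawn from the study or temporarily discontinued from the study intervention".

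Section 7.2 takes the opposite approach to poor wearers: "Patients who do not follow the prescribed bracing schedule will still be included in the study and recorded with the intention to treat principle". It also says that the data of withdrawn participants are used unless the family objects.

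**The concern.** Membership of the set depends on 90 days of wear, and a recurrence can itself end or interrupt that wear. A child found to have recurred at Day 7 or Day 30 and then cast or withdrawn has not worn the brace for the full period. The rule then selects on its own outcome, and the cases most likely to go are the early ones that were acted on. Section 9.3.3 gives early recurrence, checked before a larger trial, as the reason for the rule.

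The restriction also leaves the randomised comparison. Section 2.2 calls non-compliance the leading cause of recurrence, so the filter removes the children most at risk. A DB child who wore the bar well for 30 days and lapsed later on the standard bar (SB) is removed too, although Objective 3 concerns 30 days.

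At stake is the reported comparison that would inform the larger trial: it could understate recurrence on the DB.

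**Working it through.** **Does the text exclude these children?** Set the sections side by side. Under 9.2, inclusion needs the full 90 days of prescribed wear. Under 8.2.4.1, casting is the likely response to recurrence; under 8.2.3, withdrawal is possible. Section 7.1 keeps a child who stops a bar early in the study, and 7.2 keeps the data, but neither changes the population that 9.3.3 names. So a recurrence that is cast or withdrawn before Day 90 can be excluded. One managed by return to the SB without casting, or first found at Day 90 in an adherent child, may still count. With wear as prescribed undefined, the status of a child whose wear was interrupted for casting is open.

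**The plan's own figures.** The rule has no stated error rate or power. The only power figure is for the future trial (9.1): 62 per arm, 30% v 10%, 80% power, 5% type 1 error. It reproduces, two-sided:

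n = [1.96·√(2·0.2·0.8) + 0.8416·√(0.3·0.7 + 0.1·0.9)]² / 0.2² = (1.109 + 0.461)² / 0.04 = 61.6, rounded up to 62.

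It does not bear on the rule.

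**Effect with no assumed rate.**

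- 3 DB v 0 SB is the smallest excess that meets the rule with no control events. Remove one DB child: 2 v 0, not met.
- 4 DB v 0 SB with two DB children cast at Day 30: 2 v 0, not met.

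**Effect under assumed rates.** Take 10 per arm (9.1). Let pE and pC be the 90-day recurrence risks and L the share of recurrences lost to casting or withdrawal, equal in both arms. Then

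P(rule met) = P(X_E − X_C ≥ 3), with X_E ~ Bin(10, pE(1−L)) and X_C ~ Bin(10, pC(1−L)).

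For pE = 0.30, pC = 0.10, L = 0, sum over the control count j the product P(X_C = j)·P(X_E ≥ j+3):

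- j = 0: 0.3487 × 0.6172 = 0.2152
- j = 1: 0.3874 × 0.3504 = 0.1357
- j = 2: 0.1937 × 0.1503 = 0.0291
- j ≥ 3: about 0.003
- Total: 0.383

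| Share lost, L | 30% v 10% | 10% v 5% |
|---|---|---|
| 0 | 0.383 | 0.046 |
| 1/4 | 0.253 | – |
| 1/3 | 0.209 | 0.0185 |
| 1/2 | 0.124 | 0.0091 |
| 3/4 | 0.027 | – |

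L = 1/3 is 30/90: recurrences spread evenly over 90 days, with all those arising by Day 30 cast. With everyone counted, the rule misses a 30% v 10% excess with probability 1 − 0.383 = 0.617.

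**Non-adherence alone.** Section 2.2 cites 35% on average and 2.1 up to 61%. Applied here, they would leave 20 × 0.65 = 13 or 20 × 0.39 = 7.8 children. If non-adherence were independent of recurrence, the 0.383 would fall to 0.20 or 0.08 before any loss to casting.

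**The case against.** The strongest reply is that this is wording to reconcile, not a decision to discard recurrences. Sections 7.1 and 7.2 show an intention to keep these children and their data. Casting is only likely and withdrawal only possible. Recurrence also includes a 5-degree loss of dorsiflexion since the previous visit, and nothing says every such case is cast. That stands, and it is why the point is that cases can drop out, not that they must. But the rule names its population, and no other text puts these children back.

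Second, Objective 3 asks about a bar worn as prescribed, so an adherent analysis is partly intended. True, but for 30 days rather than 90, and wear interrupted by the outcome is not non-adherence in the sense of that objective.

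Third, section 9.3.3 says the endpoint is not meant to prove safety or efficacy, and no stopping action is tied to it. Other safeguards do not use this set: adverse events are recorded for everyone on study (8.2.5), the DSMB sees data by arm (10.1.4), and the study can be suspended for unacceptable risk (10.1.1). Section 6.3 adds: "Unblinding will occur for all participants if any severe adverse event occurs that is related to the use of the DB". Recurrence is the only severe event foreseen in 8.2.4.1. These limit the consequences for participants. None supplies a numeric threshold or an all-randomised comparison of recurrence; the DSMB charter is not among the documents.

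Fourth, 30% v 10% may be high for 90 days. The plan's 30% is a control rate for a future trial of at least two years (4.2, 9.1), and entrants here are well corrected. At 10% v 5% the rule is rarely met either way. This limits how far the probabilities can be relied on. It does not affect the 3 v 0 example, which needs no rate.

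**Conclusion.** The concern holds. As written, the only numeric harm rule in the documents can leave out early recurrences because they were acted on, and one lost DB case is enough to turn 3 v 0 from met to not met. Confidence is high on the wording. The size is conditional: at an assumed 30% v 10%, the chance of meeting the rule falls from 38% to between 25% and 2.7% as the share lost goes from a quarter to three quarters; at 10% v 5%, it falls from 4.6% to 1.9% (a third lost) or 0.9% (half). These figures assume independent children, 10 per arm and equal loss in both arms. The point should be fixed, but the other safeguards mean that recurrences would still be on record.

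**What to change.** In section 9.3.3, compare recurrence in all randomised participants by assigned arm. Count any recurrence found from Day 0 to Day 90, at a scheduled or unscheduled contact, whatever bracing or casting follows. Include randomised participants later replaced under 7.2, unless the parent asks that their data not be used. Report x/n per arm and the number not assessed at each visit. For recurrences found outside scheduled visits, record whether the blinded assessor confirmed them.

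In section 9.2, define the safety population as all randomised participants in both arms, including controls who keep their own SB. Keep the adherent set under another name as a supportive per-protocol analysis. Define wear as prescribed for it, for example by a stated sensor adherence fraction, judged only up to recurrence or Day 30, whichever comes first. That set answers Objective 3 as worded.

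The cost is a few sentences and no new visits. Events while on study are already documented under 8.2.5; recurrence after withdrawal may not be captured, which is why the number not assessed must be shown. The drawback is that recurrences due to non-wear enter the main count, and section 2.2 cites a 5- to 17-fold rise with non-adherence; the supportive analysis addresses that. The change makes the count more complete but not the rule sensitive, so the plan should also state the rule's operating characteristics at 10 per arm.
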